#### assessment.

Blood draw. Participants will be asked to provide a blood sample to measure glucose/insulin/insulin resistance and lipids/inflammation. Levels of estrogen and progesterone will also be measured. To gather this information, up to about 2-3tb of blood will be collected by a qualified individual contracted through the Magee CTRC. This will be done at all of the assessments. If women are unable to attend their assessment at Magee CTRC we will send a trained phlebotomist to their home to complete the blood draw.

Infant data: We will conduct medical chart reviews to obtain infant height, weight, and medical history during their first year of life, in accordance with the study procedures for participating women. We will also collect data on the infant gut microbiome using stool sample kits in accordance with procedures from the Center for Medicine and the Microbiome (CMM). At their 2-6 week postpartum visit, mothers will be provided with fecal sample collection kits and instructed to collect infant fecal samples, then mail them in pre-paid approved envelopes to the CMM. We will ask participants to complete 4 subscales of the Infant Behavior Questionnaire Revised (IBQ-R) at T12. This survey is designed to measure temperament in infants.

Safety alerts: We will ask participants at each follow-up (T1, T6 and & T12) about any medical events occurring between visits. Individuals enrolled in the ancillary study will also answer these questions at their T2 visit. Any medical events discussed will be logged on an interview form labeled with the participant's ID number.

COVID-19 Information: We will ask participants about any COVID-19 positive tests they had while they were in the study. Additionally, they will be asked if they received the COVID-19 vaccine. This interview form will be completed at their final assessment timepoint (12 months postpartum).

### Intervention:

By study design participants will be randomized twice over the course of their participation. Once at enrollment and again at the time of their second assessment which coincides with the end of their pregnancy. After completing the baseline assessment (T0), participants will be randomized to either the HABIT intervention during pregnancy or to usual care. Usual care consists of the care that pregnant woman usually receive from their obstetric and other providers. All women in the study will continue to receive the care they usually receive. Those in usual care will not receive any extra treatment from the study team. If they are randomized to treatment they will be assigned a coach and will immediately get started with their first session. Treatment during pregnancy will consist of up to 10 in person sessions lasting approximately 20-30 minutes. These sessions will take place at their regularly scheduled OB appointments, at our research building, or a nearby location. Participants in the HABIT pregnancy group will also receive texts and phone calls between sessions. HABIT will focus on weight, physical activity, eating and psychosocial issues. Intervention goals will emphasize adherence to healthy behaviors rather than absolute weight goals. Specifically, women will receive consultation about nutritional balance, dietary guidelines for pregnant women and advice to maintain an optimal rate of weight gain according to prepregnancy BMI. Women will use self-monitoring forms to identify and modify cues for unhealthy behaviors. Beliefs about body weight and eating during pregnancy

will be addressed and effects of physical activity on body weight, health, and mood will be included. Mood will be monitored by the EPDS questionnaire to help tailor individualized treatments. To help facilitate treatment, participants who need them will be provided with smart phones and Bluetooth enabled scales. Participants who are assigned to usual care will not have regular contact with study staff.

After participants complete the T1 assessment towards the end of their pregnancy they will again be randomized to either receive HABIT treatment postpartum or to receive usual care. All participants will be randomized again. Usual care consists of the care they would usually receive from their OB and other providers. All women will continue to receive this care, however, those assigned to usual care will not receive any additional treatment from the study. If participants are assigned to HABITpostpartum they complete a separate intervention of over the 24 weeks immediately following delivery. Treatment will consist of 12 biweekly sessions completed over the phone or in person. In person sessions will be done at the participant's home or another convenient location. Additionally, participants will receive calls and texts between sessions. Mood will be monitored by the EPDS questionnaire to help tailor individualized treatments. All participants will continue to receive their standard postpartum care from their medical team. Counseling sessions during pregnancy and postpartum will be conducted by research project staff that has, at least, masters level or equivalent degrees. Counselors will be trained by [name] prior to the start of the project. To help facilitate treatment, participants who need them will be provided with smart phones and Bluetooth enabled scales. Treatment materials are attached to the end of this application.

Treatment sessions will be audio taped for supervision.

All newly enrolled participants and any previously enrolled participant that has not yet delivered her baby will be invited to participate in the ancillary study. Women who agree to participate in the ancillary study will complete additional assessments at each HABIT timepoint and an additional assessment between delivery and 4 weeks postpartum. During these assessments they will complete the following:

Impulsive phenotypes. Participants will complete a battery of computer tasks to measure impulsivity. These tasks include the Go/No-Go Task- A computerized task in which stimuli are presented continuously and individuals must make a motor response for the go stimulus and withhold a motor response for the no-go stimulus. Stroop Color-Word Test- A computerized task in which individuals are required to name the color of a written color word while inhibiting the impulse to read the word itself. Delay Discounting Task- a computerized task in which individuals choose between smaller, immediate monetary rewards and larger, delayed monetary rewards. Wisconsin Card Sorting Test- a computerized task in which individuals have to match a target card with one of four category cards under changing conditions. Before completing these 4 computerized tasks, participants will complete a shortened practice round of the Go/No-Go Task and the Stroop Color-Word Test. During this practice round, participants will be encouraged to "go faster" when they are responding too slowly. In addition to these computer tasks, participants will also complete the Consideration of Future Consequences Scale which is a self-report questionnaire that comprises 14-items measuring a tendency to consider future consequences of behavior.

Eating behaviors. Participants will complete the self reported Power of Food Scale to assess

appetite for palatable foods and document the psychological impact of living in environments with an abundance of palatable foods.

All of these measures will be given at each HABIT timepoint as part of the ancillary study. In addition, participants will complete one additional visit outside of the regular HABIT timeline. This assessment will occur in the early postpartum period. In addition to the measures just described participants will be weighed, complete demographic and other questionnaires that are completed as part of HABIT (described above).

Participants will be asked to complete 3 follow up assessments. They will complete an assessment at the end of their pregnancy (T1), 6 months postpartum (T6) and at 12 months postpartum (T12). Individual components of these assessments are described in detail above.

Participants enrolled in the ancillary study will complete one additional follow-up assessment outside of the HABIT schedule. This early postpartum assessment (T2) will be completed between delivery and 4 weeks postpartum. Individual components of this assessment is described in detail above.

During the social restrictions placed due to COVID-19 we will be doing assessments remotely with already enrolled participants. The same assessments will be completed that are typically completed in our office. However, we are adding in 1 additional questionnaire (uploaded below) to assess how well the ancillary computer tasks worked for them on their device. The answers to this questionnaire will help us interpret this data that was collected in a different way.

During the COVID-19 shutdown of in person research we will consent new participants into the study remotely. In order to get a baseline weight, study staff may drop off a study scale outside a participant's home or another convenient location in order to get a baseline weight. The scales will be picked up at a later date outside of their home. Staff will have no direct contact with the participants. In addition, we will ask participants for any available self reported blood work results that match with the blood work that we typically get at baseline assessments. If recent results are available in medical records we will send the participant an additional medical release to pull that information.

### **Eligibility Criteria**

Women will be eligible if they: (1) have a prenatal BMI  $\geq 25$ ; (2) are at or before 17 weeks and 4 days of gestation; (3) are English speaking and (4) have a singleton pregnancy. We considered an upper limit to BMI. However, given the paucity of data on weight outcomes for women with BMIs >35, we elected not to limit BMI but will randomize women in two strata according to BMI (25-29.9 vs.  $\geq$ 30). Similarly, parity may impact perinatal weight, but intervention goals are similar for primagravidae and multiparous women. Thus, we will recruit women regardless of gravida and parity, and include these variables as covariates in all analyses.

With the approval of modification #20: (5) Identify as Black or Multiracial Black

Infants will be eligible for medical record and microbiome data collection if (1) mothers' are

enrolled into HABIT after MOD16020497-12 or (2) if we are able to reconsent their mothers' during the T1 or T2 timepoints.

### **Statistical Considerations**

First, we will use descriptive statistics and graphic displays to identify outliers, missing data and patterns of attrition, and to guide decisions about the use of transformations to satisfy the normality assumption. Next, demographic variables and baseline measures will be compared between HABITpreg and TAUpreg and between HABITpost and TAUpost using two-sample t- or Wilcoxon rank sum tests for continuous variables and chi-square or Fisher's exact tests for categorical variables. Data from women who have become pregnant again or for whom pregnancy did not result in a live birth will be excluded.

To utilize the longitudinal data collected, linear mixed-effect models will be the primary analytic tool. Mixed-effect models are useful for longitudinal datasets that contain missing observations, as anticipated in this study, under the assumption of missing at random (MAR). The MAR allows a relationship between missingness (e.g., drop-outs, missed assessments) and outcome through their mutual relationship to other covariates, such as treatment sequences or prepregnancy weight status. No residual relationship between missingness and outcome is required once covariates are taken into account. However, we also will examine patterns of missingness, and report the average effect over different missing patterns if necessary. In each mixed-effect model, we will include group, time, group by time interaction, and the stratification factor, prepregnancy BMI ( $\geq$ 30 or <30) as fixed terms. Subject will be included as a random term to account for repeated measures from the same subject. Different covariance structures will be compared to determine the best model fit.

There are 8 sequences or combinations of intervention in this SMART, which we use to define group for hypothesis testing. Time also is a generic factor, and the number of levels will depend on the outcome being modeled. For example, for weight, mood and stress, time will be a linear term beginning at baseline, and a quadratic term will be added to the model if necessary. For other outcomes, time will be a factor with 4 levels (baseline, end of pregnancy, and 6- and 12-months postpartum). We also will evaluate the need to control for the effects of potential confounds such as race, age, socioeconomic status (fixed covariates) as well as breastfeeding, smoking status and physical activity (time-varying covariates). If the coefficients for groups or group by time interactions are significant, planned contrasts will evaluate groups on weight and related outcomes at 6- and 12-months postpartum. Additionally, we will create a binary variable for 5% weight loss and use generalized mixed-effect models with the logit link to compare groups on proportions with 5% loss at 6- and 12-months postpartum.

Finally, to fully utilize a SMART design, and to evaluate the utility of using GWG as a tailoring variable, we will explore what the optimal strategy is and for which participants. A dynamic strategy is a decision rule about which intervention is best initially and what intervention follows, depending on the response status. The proposed deisgn produces HABITpreg and TAU during pregnancy, and women who do and do not meet IOM guidelines for GWG each have HABITpost and TAU postpartum, resulting in the 8 possibilities sequences.

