## **Study Objectives**

The purpose of this study is to determine the best combination of lifestyle intervention to improve maternal weight, health and psychological symptoms at 1 year postpartum.

Specific Aim 1: Determine the combination of prenatal and postpartum lifestyle interventions that optimizes maternal weight, cardiometabolic health, depressive symptoms and stress at 12-months postpartum.

Hypothesis 1: Women in HABITpreg who are assigned to HABITpost will have improved weight and secondary outcomes at 12-months postpartum relative to women who receive only HABITpreg or only HABITpost.

Hypothesis 2: Women who receive only HABITpost will have improved weight and secondary outcomes at 12-months postpartum compared to those who receive only HABITpreg or only TAUpost.

Specific Aim 2: Determine the optimal combination of interventions based on GWG that improves weight, cardiometabolic health, depressive symptoms and stress at 12-months postpartum.

Hypothesis 3: Among women who receive HABITpreg or TAUpreg and gain excessive GWG, those who are assigned to HABITpost will have improved weight and secondary outcomes at 12-months postpartum compared to those in TAUpost.

Hypothesis 4: Among women who receive HABITpost, women who met GWG goals will have improved weight and secondary outcomes compared to those who exceed GWG goals regardless of prenatal assignment.

Exploratory Aims: Evaluate the optimal sequence of interventions by prenatal weight. We will determine, for example, if the strategy of HABITpreg then HABITpost, regardless of GWG, optimizes outcomes for obese women, and if TAUpreg then HABITpost is helpful for overweight women only when GWG is excessive. Evaluate the effect of the sequence of interventions on infant risk for obesity.

Impact: This SMART is designed to identify the sequence of interventions most likely to improve maternal health at one year postpartum. Optimizing the sequence of behavioral interventions to address specific needs during pregnancy and the first postpartum year can maximize intervention potency and mitigate longer-term cardiometabolic health risks for women and their children.

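### The repeat-pregnancy exclusion has no visit limit; as written it drops T0, T1, gestational weight gain and sometimes T6 data that a later pregnancy cannot affect, and it can shift the 6- and 12-month contrasts slightly

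*Combined protocol and SAP*

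**What the plan says.** The rule is one sentence in Statistical Considerations: "Data from women who have become pregnant again or for whom pregnancy did not result in a live birth will be excluded". It names women, not visits, and no other section narrows it.

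The same section then picks a linear mixed model and gives the reason: ("Mixed-effect models are useful for longitudinal datasets that contain missing observations, as anticipated in this study, under the assumption of missing at random (MAR"). Subject is a random term, and on the covariance it says "Different covariance structures will be compared to determine the best model fit".

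In the models of weight, mood and stress, the plan is that "time will be a linear term beginning at baseline, and a quadratic term will be added to the model if necessary". The remaining outcomes are handled differently: "For other outcomes, time will be a factor with 4 levels". If the group or group-by-time terms are significant, "planned contrasts will evaluate groups on weight and related outcomes at 6- and 12-months postpartum". A second analysis will "create a binary variable for 5% weight loss" and compare groups at the two postpartum visits.

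Under Study Design & Methods, T0 and T1 fall in the index pregnancy and T6 and T12 are postpartum. GWG is computed from the last weight before delivery and is named there as a dependent variable. Under Intervention, the first randomisation follows T0 and the second follows T1, so any repeat pregnancy comes after both. Hypothesis 4 in Study Objectives compares groups defined by GWG: "women who met GWG goals will have improved weight and secondary outcomes compared to those who exceed GWG goals".

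**The concern.** Setting aside a weight measured during a new pregnancy is reasonable. Removing everything the woman contributed before that pregnancy is a different step, and it has three consequences.

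- **Valid data are lost.** T0, T1 and GWG are fixed before the index delivery. T6 is also unaffected when conception follows it.
- **The comparison is conditioned on a post-randomisation event.** The groups compared at 6 and 12 months become women who did not conceive again, and repeat pregnancy may relate to both weight and group.
- **The wording is open.** One analyst may drop women and another may drop visits, and both could claim to follow the plan.

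The whole-woman rule also gives up the feature for which the mixed model was chosen, its ability to use women with some visits missing. No sensitivity analysis that keeps these women is described.

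**Working it through.** **Data lost (from the documents alone).** There are 4 assessments. Conception after T6 removes 3 valid assessments (T0, T1, T6) plus GWG in order to drop one affected visit. Conception before T6 removes 2 valid assessments (T0, T1) plus GWG.

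**When a contrast shifts.** Let *p* be the share of a group excluded and *D* the mean weight of excluded minus retained women, had no new pregnancy occurred. The retained mean equals the full mean minus *pD*, so the contrast between groups 1 and 0 shifts by −(*p*₁*D*₁ − *p*₀*D*₀). This is zero if *D* = 0 in both groups, or if *pD* is the same in both.

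**Assumed inputs.** The plan gives no rate, SD or effect, so all of these are assumptions. True difference −2 kg at T6 and −3 kg at T12; mean change from baseline 0/+9/+3/+2 kg over the four visits; SD of change 4/5/6 kg at T1/T6/T12; correlation 0.7 between adjacent visits and 0.49 between T1 and T12. Half of the repeat pregnancies begin before T6 and depend on T1 change; half begin after T6 and depend on T6 change. Log-odds are 0.5 or 1.0 per SD of that change.

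**Hand calculation.** For a fairly rare event, *D* is about the log-odds times the mean covariance factor. At T12 this factor is (0.49×6 + 0.7×6)/2 = 3.57 kg.

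- 10% v 4%: 0.06 × 0.5 × 3.57 = 0.11 kg; 0.06 × 1.0 × 3.57 = 0.21 kg.
- 6% v 4%: 0.02 × 0.5 × 3.57 = 0.04 kg; 0.02 × 1.0 × 3.57 = 0.07 kg.
- One common relation, 7% overall, arm contrast. Only conceptions after T6 (3.5%) respond to the 2 kg T6 effect. The log-odds differ by 0.5×2/5 = 0.2 or 1.0×2/5 = 0.4, so the rates differ by about 0.035×0.2 = 0.007 or 0.035×0.4 = 0.014. With a factor of 0.7×6 = 4.2 kg the shift is 0.007×0.5×4.2 = 0.015 kg or 0.014×1.0×4.2 = 0.06 kg.

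**Simulation, whole-woman exclusion, shift at T12.**

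| Scenario | Shift (kg), log-odds 0.5 to 1.0 |
|---|---|
| 10% v 4% | about 0.1 to 0.2 |
| 6% v 4% | 0.04 to 0.07 |
| Common relation, 7% overall, arms (6.2% v 7.4% at log-odds 1.0) | about 0.02 to 0.05 |
| Common relation, 7% overall, Hypothesis 4 groups | about 0.05 to 0.19, on a contrast of about −4.8 kg |
| Rates forced equal, 7% v 7% | 0.02 or less |
| 10% v 4%, unrelated to weight | about 0 |

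The Hypothesis 4 row takes 45-63% of women as exceeding the GWG guideline, the range in Scientific Background. Swapping the arms reverses the sign. In a separate simulation with different assumed inputs, rates near 10% in both groups but relations of opposite sign (log-odds −0.7 and +0.7 per 6 kg) shifted T12 by 0.55 kg. That shows equal rates alone are not a safeguard.

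**Precision.** If repeat pregnancy is unrelated to weight, excluding 7% multiplies the standard error by 1/√0.93 = 1.037. Visit-level censoring raises it by at most 1.0% at T6 and 2.4% at T12.

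**Does visit-level censoring work?** At 10% v 4%, with covariance estimated from the data and log-odds 0 to 1.0:

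| Time term | Covariance | Shift after censoring (kg) |
|---|---|---|
| 4-level factor | unstructured | at most 0.01 |
| 4-level factor | random intercept | T12: 0.04 to 0.07 at log-odds 0.5 to 1.0 |
| linear | unstructured / random intercept | T12: up to 0.05 / 0.14 |
| quadratic | unstructured / random intercept | T6: up to 0.10 / 0.11 |

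The linear and quadratic maxima occur when repeat pregnancy is unrelated to weight, where whole-woman exclusion shifts nothing. They depend on the assumed mean curve, which a straight line or parabola fits poorly. If conception depends on a T6 weight that is itself censored, missing at random fails: the 4-level factor with unstructured covariance then leaves 0.03-0.08 kg, against 0.13-0.25 kg at T12 under exclusion.

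**The case against.** **The clause may already mean visits.** It can be read as covering only data collected once a woman is pregnant again. That stands as a possible intention, so the documents do not prove that the sponsor will delete whole women. But nothing says so, and the pairing with pregnancies that did not end in a live birth, where a whole-woman exclusion is natural, points the other way. A clarification is needed on either reading.

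**The shift is small and conditional.** This stands. A reader might infer that the exclusion biases the trial's results. The documents do not support that: they give no repeat-pregnancy rate, no difference between groups and no relation to weight. The opposite shortcut fails too. A relation to weight alone is harmless only if the rates are equal, and one common relation can separate the rates when treatment changes weight or when groups are defined by GWG.

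**GWG matters less than it seems.** Partly fair. GWG is named as a dependent variable, but Hypotheses 1-4 concern 12-month outcomes and no GWG outcome model is specified.

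**The remedy reaches into the time term.** It does, and for a reason: changing the clause alone can introduce a distortion that exclusion does not have. Still, the figures for this depend on an assumed mean curve. Larger ones arise only if the covariance is held at its true value, which no analyst can do, so they are not relied on here.

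**Conclusion.** The point holds as a cheap improvement, not as a demonstrated bias. The clause has no visit limit, and followed as written it discards measurements that a later pregnancy cannot affect. That part needs no assumptions.

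The effect on the 6- and 12-month contrasts is conditional and its size is unknown. In most of the assumed scenarios it is 0.2 kg or less at T12, against an assumed true arm difference of 3 kg; it grows larger only with higher or more unequal rates, or if the relation to weight itself differs markedly between groups. If repeat pregnancy is unrelated to weight, the cost is precision alone.

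Visit-level censoring is better under missing at random, and it leaves a smaller residual shift in the failure of that assumption examined here. The gain is secure only with categorical time and an unstructured covariance.

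**What to change.** Replace the repeat-pregnancy part of the sentence with:

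> Weight and related measures taken after conception of a subsequent pregnancy are set to missing; all earlier measurements, including GWG, are kept. The target is the outcome had no new pregnancy occurred.

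Adopt with it:

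- For the weight model, use time as the 4-level factor already planned for other outcomes. Specify an unstructured covariance, with a simpler structure only if that model does not converge. Listing it as one candidate among several is not enough.
- Report repeat pregnancies by arm and by GWG group.
- Keep whole-woman exclusion as a sensitivity analysis.
- Leave the no-live-birth exclusion as it is, and report its counts by prenatal arm.

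Costs: one clause, one estimand sentence, the time and covariance terms, and a visit-level flag. Group-by-time mean parameters for 8 groups rise from 8×2 = 16 (linear) or 8×3 = 24 (quadratic) to 8×4 = 32. The censored visits rely on missing at random. Conception can be dated only approximately, from the pregnancy questionnaire and the between-visit medical-events interview, because the maternal chart review described covers the index pregnancy. In the 5% weight-loss model, which has outcomes only at 6 and 12 months, the change recovers only the T6 value of women who conceive after it.

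### The only missing-data analysis beyond MAR averages over dropout patterns with no identifying restriction, so for women lost after T1 it either extends pregnancy gain past delivery or cannot reach 12 months

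*Combined protocol and SAP*

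**What the plan says.** All of this is in Statistical Considerations unless noted.

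- The linear mixed model is the primary tool and relies on MAR. Its fixed terms are listed: "we will include group, time, group by time interaction, and the stratification factor", the last being prepregnancy BMI. No term for missing-data pattern appears.
- Missing data are first examined descriptively, to "identify outliers, missing data and patterns of attrition".
- The one analysis beyond MAR is to examine patterns of missingness and "report the average effect over different missing patterns if necessary". The plan does not say what a pattern is, how patterns are weighted, what identifies late outcomes in women lost early, or what makes the step necessary.
- On time coding, the plan says that "for weight, mood and stress, time will be a linear term beginning at baseline". Curvature is optional: a squared term may be brought in where the fit calls for it. The remaining outcomes treat the four assessments as separate categories.
- Study Design & Methods sets T0 at 16 weeks or less, T1 at 32 to 40 weeks, and T6 and T12 at 6 and 12 months postpartum. The Intervention section places the second randomization after T1.

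**The concern.** An effect averaged over patterns at 12 months needs a 12-month effect within each pattern. A woman who leaves after T1 has two study visits, both in pregnancy. Anything said about her at one year postpartum therefore comes from the model.

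A straight line treats delivery as if it did not happen and continues the pregnancy gain for another year. A curve or a visit factor has nothing to work with.

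The check would be reached for when dropout looks troublesome, which is when a sound sensitivity analysis matters most. Under linear time it can move away from the MAR result even when dropout is completely random. A gap between the two would then say nothing about MAR. Unequal loss between arms is conceivable, since "Participants who are assigned to usual care will not have regular contact with study staff", but the documents give no dropout rate for any arm.

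**Working it through.** The plan states no figure on this point, so there is nothing to reproduce. The check has two parts.

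**1. Is the T12 mean identified within a pattern, from study visits alone?**

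| Visits seen | Linear | Quadratic | Visit factor |
|---|---|---|---|
| T0 | no | no | no |
| T0, T1 | yes, by extrapolation | no | no |
| T0, T1, T6 | yes, by extrapolation | yes, by extrapolation | no |
| T0, T1, T12 | yes | yes | yes |
| All four | yes | yes | yes |

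Two points fix a line but not a quadratic. A factor level that is never observed in a pattern has no estimate there.

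**2. What does linear extrapolation do?**

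Assumed timing: T0 at 14 weeks, T1 at 36, delivery at 40. The visits then fall at 0, 22, 52 and 78 weeks after T0.

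- Multiplier on the T0-T1 change: 78/22 = 3.5. With T0 at 8 to 16 weeks and T1 at 32 to 40, it runs from 84/32 = 2.6 to 76/16 = 4.75.
- An assumed 11 kg gain by T1 becomes 11 × 78/22 = +39 kg at 12 months.

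Now take a prenatal contrast with an assumed -2 kg at T1 and zero at every other visit, so the truth at T12 is zero.

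- Women lost after T1: -2 × 78/22 = -7.09 kg.
- Women with all four visits: mean time 38, sum of squares 3496, slope (-16 × -2)/3496 = 0.00915 kg per week. Modelled change over 78 weeks is +0.71 kg. Modelled level at T12 is -0.5 + 40 × 0.00915 = -0.13 kg.
- Pattern average = (1 - d) × completer contrast + d × (-7.09), where d is the share lost after T1 and everyone else is complete:

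| d | Change from T0 (kg) | Level at T12 (kg) |
|---|---|---|
| 10% | -0.07 | -0.83 |
| 20% | -0.85 | -1.53 |
| 30% | -1.63 | -2.22 |

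**Other pattern definition.** Pool all dropouts into one line, half lost after T1 and half after T6. The weighted mean time is 48/2.5 = 19.2 and the sum of squares is 914.4. The slope is (2.8 × -2)/914.4 = -0.0061. The dropout contrast is -0.48 kg (change) or -1.16 kg (level). If 80% of the dropouts leave after T1, it is -2.1 to -2.6 kg. With 20% dropout in total and the half-and-half split, the overall average is 0.8 × 0.71 + 0.2 × (-0.48) = +0.48 kg (change) or 0.8 × (-0.13) + 0.2 × (-1.16) = -0.34 kg (level).

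**Contrasts within a prenatal arm.** T1 precedes the second randomization, so women lost after T1 contribute an expected difference of zero. With equal dropout the contrast is unbiased under the null. Otherwise, if everyone else is complete, it shrinks to (1 - d) times the completer contrast.

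Unequal dropout is different. Take visits at 0, 20, 50 and 76 weeks and assumed mean gains over T0 of 25, 12 and 10 lb. The line through T0 and T1 gives 25 × 3.8 = 95 lb at T12, and the completer line gives 13.5 lb. If one arm loses 10% after T1 and the other 20%, a true zero becomes 0.1 × (13.5 - 95) = about -8.2 lb.

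**The case against.** The strongest reply is that the plan never commits to the model being criticised. The listed fixed terms contain no pattern-by-time term. The sentence could mean pooling all incomplete women, and an identifying restriction is neither stated nor excluded. That stands. It is why the size must be given as a range, and why the pooled result above belongs beside the other.

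Several further points also stand:

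- A 12-month effect that cannot be estimated is not a false effect. Under visit-factor time the check returns nothing for that pattern, or falls back on women with T12 data.
- At 10% loss the distortion on the change scale is negligible. With no dropout at all, the straight line already gives +0.71 kg on that scale, so part of the problem is the line itself.
- The check supplements the MAR model, which remains primary.
- Dropout that differs by arm does not by itself violate MAR. The plan says so, naming treatment sequence among the covariates that may explain missingness.
- Chart weights in pregnancy, and an early postpartum weight for ancillary-study participants, are also collected. The plan does not say whether they enter the model. They could identify a curve, but only from pregnancy and the first four weeks after delivery.

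None of this supplies the missing restriction. Every available reading still needs something the plan does not state before the check can speak about 12 months in women lost after T1.

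**Conclusion.** The point holds as a weakness in the method, and it goes beyond missing detail. With the plan's own time coding, averaging over patterns yields an extrapolation across delivery or no 12-month estimate for women seen only at T0 and T1. Neither is a usable test of departure from MAR.

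If women lost after T1 form their own pattern, the false contrast across prenatal arms is up to about 0.8 kg at 10% loss, 1.5 kg at 20% and 2.2 kg at 30%. These figures assume the visit timing above and a 2 kg difference at T1 only. Pooling dropouts makes the distortion much smaller. Postpartum contrasts within a prenatal arm are unbiased under the null when dropout is equal, and otherwise attenuated.

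A reader might infer that the trial will certainly report false 12-month effects, or that its type I error is inflated by a known amount. The documents support neither. The step is conditional and secondary, its pattern definition is open, and a false-positive rate would need a sample size, variances and a dropout rate that the documents do not give. Nor do they show that informative dropout is likely.

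**What to change.** - Code time as visit (T0, T1, T6, T12) for weight, mood and stress, as already planned for the other outcomes. Keep the MAR mixed model as the primary analysis.
- Replace the pattern-average sentence with one prespecified sensitivity analysis that is always run and needs no extrapolation in time: multiple imputation under MAR, with a delta shift added to missing T6 and T12 values, varied separately by arm until the conclusion changes (tipping point).
- Reference-based imputation, or a pattern-mixture model with its restrictions written out, would be an acceptable alternative.
- State how women lost before T1 are handled. They have no second assignment, so they have no observed group among the eight sequences and no matching postpartum reference group.

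The cost is revised wording, some extra programming, three time contrasts per group in place of one, and slightly wider intervals. No new data are needed.
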